At our institution, a majority of DCCV are performed in the electrophysiology lab (EP lab). Sedation is delivered by either a CRNA under the supervision of an anesthesiologist, or by an EP lab RN under the direction of an electrophysiologist. The medication choice for sedation has traditionally been at the discretion of the supervising physician. The medication choices for sedation at our institution have historically been either propofol or methohexital. Each medication has specific properties and pharmacokinetics that affect duration of action, hemodynamic changes, and respiratory depression.⁷ Although these medications have been compared in other settings, such as during fracture and dislocation reduction in the ED,⁸ there are limited studies on the use of methohexital for sedation during cardioversion. The largest study was a cost effectiveness cohort study of 1,473 patient undergoing an elective cardioversion using methohexital dosing of 0.4-0.6 mg/kg.⁹ Although this was a cost effectiveness study, the safety and cost savings lead the authors to continue to use it for their cardioversions. To date there has been only one, small, randomized controlled trial comparing propofol and methohexital for DCCV.¹⁰ There were only 10 patients per group in this three group randomized

controlled trial. Although it found no significant difference in the mean arterial pressure or time to awakening, there was a trend to quicker recovery in the patients receiving methohexitol.

We intend to perform a randomized, open-blinded, prospective study to evaluate the timeliness and safety of DCCVs when using methohexitol when compared to the more often used propofol. If there is a significant reduction in time to recovery from induction, the use of methohexitol as compared to propofol can significantly decrease healthcare costs based on staff utilization and cost of medications.¹⁰

Objectives

Hypothesis:

We theorize that the use of methohexitol during cardioversion will result in a shorter time to effective sedation and time to full recovery when compared to the use of propofol. This will change how sedation is approached for elective cardioversions.

Primary Hypothesis:

1. The mean time to recovery from sedation during a cardioversion using methohexitol for sedation will be significantly shorter than the recovery time using propofol for sedation, as evidenced by a short time from initiation of induction to a score of 2 on the Ramsay Sedation Scale.

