2. The mean time to a Ramsay score of 5-6 will be significantly shorter using methohexitol than the time to the same sedation level using propofol

Secondary Hypothesis:

1. There will be no significant increase in adverse events associated with the use of methohexitol when compared with propofol.

Methods and Measures

Design

We will perform a randomized, open-blinded, prospective study on all patients present for DCCV who meet inclusion criteria and consent to enrollment in the study. Patients will be randomized to sedation with bolus dosing of either propofol or methohexitol

Setting

This will be a single site study at a large academic medical center – Wake Forest Baptist Medical Center

Subjects selection criteria

- **Inclusion Criteria**

We will select all patients over the age of 18 who present to Wake Forest Baptist Medical Center for a direct current cardioversion for treatment of paroxysmal or persistent atrial fibrillation as well as atrial flutter.

- **Exclusion criteria**

Patients with sedation for transesophageal echocardiogram within 30 minutes of DCCV will be excluded. Hemodynamically compromised patients (as defined by hypotension <90/50 mmHg, altered mental status, shock, ischemic chest discomfort, or heart failure) will also be excluded.

Sample Size

We intend to randomize a total of 150 patients to either propofol or methohexitol

The following calculations have been used to establish the sample size for the full study

According to a study evaluating bolus dosing of propofol as outlined above, the time to recovery was 10.98 ± 2.51 min.¹¹

We will presume that a significant difference in time to recovery will be 2 minutes based on the average recovery time of 9 minutes when using methohexitol in a small randomized controlled trial utilizing bolus dosing.¹²

Estimated sample size for two-sample comparison of means

Null hypothesis: $m_1 = m_2$, where: m_1 is the mean value in population 1

m_2 is the mean value in population 2. Mean time to recovery from sedation with propofol is no different than mean time to recovery from sedation with methohexitol.

Alternative hypothesis: $m_1 \neq m_2$. Mean time to recovery from sedation with propofol is different than mean time to recovery from sedation with methohexitol

Assumptions:

Alpha = 0.05 (two-sided)

Power = 0.8

Effect size = difference in mean value of the outcome variable population 1 and population 2 = 2 minutes

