Standardized effect size = effect size \div standard deviation = $2 \text{ min} \div 2.51 \text{ min} = 0.797$

Based on the above calculations we will need to review at least 50 patients in a 1:1 equal distribution between propofol and methohexitol. We will randomize 150 patients to ensure significance.

Intervention and Interactions

All patients presenting to the EP lab will be informed about the study and those who agree to participate will sign informed consent.

Clinical data will be collected from electronic medical records of Wake Forest Baptist Health (WakeOne, Muse). Data that are not available electronically be obtained from the patient and/or accompanying

family members. The following clinical data will be collected: name, age, MRN, gender, ethnicity, race, height, weight, BMI, sodium, potassium, calcium, creatinine, creatinine clearance by Cockroft-Gault method, magnesium, presence or absence of antiarrhythmic medications (Na Channel blocker, Beta Blocker, Potassium Channel Blocker, Calcium Channel Blocker, Digoxin), CHA2DS2-VASC score, HAS-BLED score, presence of Watchman device, type of anticoagulation, INR if on warfarin. In addition to this we will collect parameters from the most recent echocardiogram (<1 year): Left atrial (LA) diameter, LA volume index, LVEDV, LVESV, EF, presence of a pre-procedure TEE. We will include the following parameters from the clinical history: HTN, HFrEF (<50%), HFpEF (>50%), prior stroke, DM, COPD, thyroid disorder, smoking status, drinking history, ASA Status, and Arrhythmia type.^{13,14}

Using the randomization tool within REDCap, our secure data storage program, stratified by sex, ASA status, and presence or absence of HFrEF (EF <50%), patients will be randomized to boluses of either methohexitol or propofol. Methohexitol will be given at an initial dose of 0.5 mg/kg, followed by 10 mg every minute after 2 minutes, if adequate sedation is not achieved. Propofol will be given at an initial dose of 0.8 mg/kg followed by 20 mg every minute after 2 minutes, if adequate sedation is not achieved.^{9,15} The CRNA or anesthesiologist will draw up the pre-specified dose.

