Predictor Variables: name, age, MRN, gender, ethnicity, race, height, weight, BMI, sodium, potassium, calcium, creatinine level, creatinine clearance, magnesium, CrCl by Cockcroft gault, presence or absence of antiarrhythmic medications (Na Channel blocker, Beta Blocker, Potassium Channel Blocker, Non-dihydropyridine CCB, digoxin), CHA₂DS₂-VASC score, HAS-BLED score, presence of Watchman, anticoagulation use: DOAC, Warfarin, ASA, Plavix, recent INR. Parameters from the most recent echocardiogram (<1 year): Left atrial (LA) diameter, LA volume index, LVEDV, LVESV, EF, pre-procedure TEE, Hypertension, congestive heart failure, stroke, diabetes, COPD, previous thyroid disorder, smoking status, alcohol use, ASA Status, Arrhythmia type (Atrial Fibrillation with RVR (HR >100 bpm), Atrial

Fibrillation with controlled VR (HR <100 bpm), Atrial Flutter with 2:1 block, Atrial Flutter with variable block), medication for sedation, final medication dose

Outcome variables: T1 time to LOC, T2 time to first shock, T3 time to eyes open, T4 time to recovery, HRinduction, HRshock, HR1, HR3, HR5, HR7, HR9, HR10, HR15, HR20, HR30, SBP (1,3...etc.), DBP (1,3...etc.), MAP (1,3...etc.), RR (1,3...etc.), SpO2 (1,3...etc.), NumCV, MaxEnergy, DCCVsuecess, MedDose(mg/kg), Redose,

Safety measures: Bradycardia, Hypotension, Vasopressor use, Hypoxemia, Jaw Thrust, Bag Mask, Invasive Airway, Apnea, SIVAsensitivity, PainVAS, UnpleasantVAS.

Analytical Plan

Continuous variables will be summarized with mean (standard deviation) or median (interquartile range) depending on the normality of the data and compared using student's t-test or Wilcoxon rank-sum test, respectively. Categorical variables will be summarized with counts (percent) and compared using chi-square tests. Multivariate linear regression analysis will be used to examine relationships further and adjust where necessary.

Potential Limitations:

Inability to double blind the treatment: due to the difference in appearance between methohexitol (clear) and propofol (milky) we are unable to blind the administrator of the medication. However the researcher collecting the information and the patient will be blinded to treatment allocation by obscuring the patient's arm from the patient and the sedation type from the data collector. The selection of energy will be determined prior to randomization and selection for medication.

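### The recovery-time comparison (T4) is hypothesised and sized on means, but the Analytical Plan lets it switch to medians and a rank test and leaves the stratification factors out of the comparison

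*Combined protocol and SAP*

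**What the plan says.** Under Primary Hypothesis, the first statement is that "The mean time to recovery from sedation during a cardioversion using methohexitol for sedation will be significantly shorter" than with propofol. Sample Size writes the null in the same terms, "Mean time to recovery from sedation with propofol is no different than mean time to recovery from sedation with methohexitol", and sets "Effect size = difference in mean value of the outcome variable population 1 and population 2 = 2 minutes". Outcome Measures names T4, from initiation of sedation to a Ramsay score of 2, as the primary outcome.

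The Analytical Plan treats all continuous variables alike. They are summarised by mean (SD) or median (IQR) and tested "depending on the normality of the data and compared using student's t-test or Wilcoxon rank-sum test, respectively". T4 has no rule of its own. No normality test or threshold is named, and the plan does not say whether arms, pooled data or residuals are examined.

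Under Intervention and Interactions, allocation is "stratified by sex, ASA status, and presence or absence of HFrEF (EF <50"%). The Analytical Plan does not mention these factors. It adds a linear regression for looking further at relationships and adjusting if needed, without naming an outcome or choosing covariates. The Variables section has a long predictor list that covers or closely matches the stratification factors. It ends with "medication for sedation, final medication dose". The same section also lists dose per kg and re-dosing among the outcomes.

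**The concern.** Two features of the primary analysis do not follow from the design.

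First, the quantity estimated depends on how the data look. On the t-test branch the plan gives a mean and SD per arm, from which a difference and interval can be worked out. On the Wilcoxon branch it gives medians and a rank test. A rank test does not test equality of means when the two arms differ in shape, and it yields nothing to compare with the 2 minutes. Recovery times are often right-skewed, so the second branch is a realistic outcome.

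Second, factors judged important enough to stratify on are left out of the comparison. If they predict T4, balancing them makes the arms more alike than the unadjusted standard error assumes. The test is then conservative and the interval too wide.

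At stake are the match between test and hypothesis, and a pre-specified estimate in minutes at the precision the design already provides. The covariates are also unchosen while a post-randomisation quantity, final dose, sits in the predictor list, so its exclusion should be made explicit.

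**Working it through.** **Inputs from Sample Size.** Difference 2 min, SD 2.51 min, two-sided alpha 0.05, power 0.80, 1:1 allocation, 150 randomised (75 per arm).

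**The plan's own figure.** n per arm = (1.960 + 0.842)² × 2 × 2.51² / 2² = 24.7, so 25 per arm and 50 in total. This reproduces the stated minimum, and it is a calculation for means.

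**Power at 75 per arm.** SE = 2.51 × √(2/75) = 0.410. Power = Φ(2/0.410 − 1.96) = Φ(2.92) = 99.8%. Adjustment does not lower this materially (at least 99.7% in simulation).

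**Precision.** The share of T4 variance explained by the strata (R²) is not in the documents, so a range is assumed.
- Unadjusted: t(0.975, 148) × 0.410 = 1.976 × 0.410 = 0.81 min.
- Adjusted, with ASA as one two-level term: t(0.975, 145) × 0.410 × √(1 − R²).

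| Assumed R² | 0% | 10% | 20% | 30% |
|---|---|---|---|---|
| Adjusted half-width (min) | 0.81 | 0.77 | 0.72 | 0.68 |

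Four ASA classes (143 degrees of freedom) give the same figures to two decimals. With simple randomisation, chance imbalance makes them 0.82, 0.78, 0.73 and 0.69.

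**Type I error of the unadjusted comparison.** If the strata were perfectly balanced, the true standard error would shrink by √(1 − R²) while the estimated one would not. The error is then about 2 × [1 − Φ(1.976/√(1 − R²))] = 3.7, 2.7 and 1.8% at R² of 10, 20 and 30%. Simulation with assumed blocks of 4 gives 4.2, 3.4 and 2.3% with ASA in four classes (16 strata), and 4.0, 3.1 and 2.4% with two classes (8 strata). The adjusted analysis stays at 4.7 to 5.4%. The documents give no block size; with simple randomisation the unadjusted test is at about 5%.

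**The test switch.** The plan names no criterion, so Shapiro-Wilk at 5% in either arm is assumed, with 75 per arm.
- How often Wilcoxon is chosen: about 10% of trials if T4 is normal, and 77–78% if it is lognormal with the protocol's mean 10.98 and SD 2.51.
- Same shape in both arms, no effect: the rule rejects 5.0–5.6%.
- Equal means but different shape (assumed +6 min tail in 5% of one arm and 20% of the other): about 6–8%, against about 5% for Welch.
- Means differing by 0.9 min through that tail alone, (0.20 − 0.05) × 6 = 0.9: the rule detects 35% or 34% (core SD 2.14 or 2.51), Welch 48% or 41%.
- Means differing by 0.9 min through a plain shift, with a common 12.5% tail: the rule detects 53% or 42%, Welch 47% or 40%.

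The last two lines point in opposite directions. Which test has more power depends on the shape assumed.

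**The case against.** The strongest reply is that little is at risk. The unadjusted comparison is valid, power for 2 minutes is about 99.8%, and the switch holds its level when the arms share a shape. A reader might infer that the normality rule generally inflates error or costs power. The documents do not support that. Both arms share the same re-dosing timing and no re-dosing rates are given, so a tail in one arm only is an assumption. With a common shape the rule can beat Welch. This part of the reply stands: the case for fixing the test rests on its match to the stated hypothesis.

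A reader might also infer that the regression would adjust for dose and so remove much of the treatment effect. Final dose is set after randomisation. The starting doses per kg also differ by arm ("Methohexitol will be given at an initial dose of 0.5 mg/kg"; "Propofol will be given at an initial dose of 0.8 mg/kg followed by 20 mg every minute after 2 minutes"), so without re-dosing dose per kg is the same variable as arm. But the predictor list also holds name, record number and the study drug itself, so it reads as a data dictionary. No sentence puts dose in a T4 model, and the regression is not said to be primary. No size can be claimed for that harm; a one-line safeguard is enough.

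It is fair, too, that the precision gain at 10% explained variance is only 0.04 min (about 2.5 seconds), and that no document gives an R². The gain is uncertain, but so little is paid for it that this does not argue against adjusting. Finally, the missing interval affects mainly the Wilcoxon branch, since the other branch gives means and SDs by arm.

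**Conclusion.** The point holds in a limited form and should be acted on. The hypothesis, null and sample size concern mean T4, while the analysis rule may deliver a rank test and medians with no mean difference to set against 2 minutes. This follows from the text and needs no assumption.

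The unadjusted comparison also leaves unused the precision that stratification may offer: from nothing up to 0.13 min of half-width (0.81 to 0.68) over an assumed R² of 0 to 30%. Under assumed blocks of 4, its type I error falls to about 4, 3 and 2% at R² of 10, 20 and 30%. That makes it conservative; it does not make it invalid.

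The rule departs from the null on means only if the arms differ in shape, with 6–8% rejection under the assumed tails and normality check. Detection of the 2-minute target is not threatened.

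**What to change.** In the Analytical Plan, state that the primary T4 analysis, whatever the normality check shows, is a linear regression of T4 on arm plus the stratification factors as used at randomisation: sex, ASA status and HFrEF. The Baseline Data form records ASA in four classes, and the protocol does not say whether they were merged for allocation. Say which coding was used, and let sparse classes be merged only by a rule fixed in advance. Report the adjusted mean difference in minutes with its 95% CI, preferably with robust standard errors. Report Wilcoxon and medians (IQR) as a sensitivity analysis.

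Add one sentence that variables arising after randomisation (final dose, re-dosing, number of shocks) do not enter this model.

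The cost is wording, a little more analysis work, and three further degrees of freedom with ASA in two classes or five with four. The factors are already collected before treatment. If they explain nothing, the half-width is 0.81–0.82 min against 0.81. The sample size and trial conduct do not change.

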blood pressure (SBP), diastolic blood pressure (DBP), mean arterial pressure (MAP) respiratory rate (RR) and oxygen saturation (SpO₂) will be measured through a mounted patient monitor (Phillips Intellivue MP5, Koninklijke Philips N.V, Amsterdam, Netherlands). The above parameters will be measured at induction, before the shock, and every minute after the shock for the first 10 minutes, 15 minutes, 20 minutes and 30 minutes.

The following time intervals for the procedure will be recorded in seconds: (T1) time from end of injection to loss of conscious [RSS 5-6]; (T2) Time to first shock; (T3) time to eyes opening [RSS 3]; (T4) Time the ability to answer simple questions of age and name [RSS 2]

Outcome Measures

The primary outcome to be measured will be (T4) the time from initiation of sedation to full recovery (RSS of 2) as evidenced by the ability to answer the questions “What is your name and what is your age?”¹⁶ We will start the timer at the initiation of induction.

Secondary time based outcomes will include: (T1) time from end of injection to loss of conscious [RSS 5-6]; (T2) Time to first shock; (T3) time to eyes opening [RSS 3]. Secondary hemodynamic outcomes will be vital status parameters (HR, SBP, DBP, MAP, RR, SpO₂) at induction, prior to first shock, then 1, 3, 5, 7, 9, 10, 15, 20, and 30 minutes after first cardioversion.

Procedural parameters measured will be: Number of DCCV, max energy used for successful DCCV, success of DCCV, dosage of medication (mg/kg), need for re-dosing.

Safety endpoints will be: evidence of bradycardia (HR <60 bpm), Hypotension (decrease in SBP ≥20%, hypoxemia (SpO₂ nadir <85%), need for advanced airway maneuvers (jaw thrust/chin lift, or bag mask ventilation), apnea (respiratory arrest ≥ 20 seconds), Severity of World SIVA averse sedation event.¹⁸

Patient experience endpoints will be measured after full recovery: recall of pain at injection site (visual analog scale, VAS)¹⁹, recall of anything unpleasant about the procedure (VAS). These are 100 mm lines that are anchored with “no pain” or “no distress” on one end and “worst imaginable pain” or “worst imaginable distress” on the other end. The patient will utilize the computerized VAS within REDCap to mark the appropriate level.

Variables

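### World SIVA severity is an ordered grade, but the plan's only rule for categorical variables is a chi-square test that ignores order; name an ordinal comparison and define the levels

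*Combined protocol and SAP*

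**What the plan says.** Under Outcome Measures, the safety endpoints end with "Severity of World SIVA averse sedation event". In the Variables section the corresponding item appears as "SIVAsensitivity", with no levels or coding.

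The Analytical Plan offers three tools:

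- Continuous variables are "compared using student's t-test or Wilcoxon rank-sum test, respectively", depending on normality.
- For the rest, "Categorical variables will be summarized with counts (percent) and compared using chi-square tests".
- Beyond that, "Multivariate linear regression analysis will be used to examine relationships further and adjust where necessary".

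No trend test, rank test for ordered categories or ordinal model is named. The safety hypothesis under Objectives reads: "There will be no significant increase in adverse events associated with the use of methohexitol when compared with propofol". No event rate, margin, effect size or power accompanies it.

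**The concern.** A severity grade carries its information in its order. Pearson's chi-square gives the same result if the mild and severe columns are swapped, so it cannot use that order. With two arms and k levels it has k − 1 degrees of freedom, and the more finely severity is graded, the more thinly a one-directional difference is spread.

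The safety hypothesis is about an increase, and the expected conclusion is that there is none. If methohexital did shift patients towards worse grades, the stated test would be more likely to return a non-significant result than an ordinal test on the same data.

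The plan also does not say how a patient without any event is coded. That needs settling before the endpoint can be analysed by any method.

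**Working it through.** **Inputs from the documents.** The Sample Size section gives a two-sided alpha of 0.05, power 0.8, a difference of 2 min, an SD of 2.51 min, at least 50 patients needed in a 1:1 split, and 150 to be randomised. Hence 150 / 2 = 75 per arm. Applying the same alpha to the safety comparison is an assumption.

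**The plan's own figure.** n per arm = 2(1.960 + 0.842)² × 2.51² / 2² = 2 × 7.85 × 6.30 / 4 = 24.7, so 25 per arm and 50 in total. The stated 50 reproduces. It concerns time to recovery only; no power is stated for any safety endpoint.

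**Assumptions for SIVA severity.** The documents supply none, so a range is used: 3 to 5 levels, with no event as the lowest and 50% to 90% of the reference arm in it. The other arm is shifted by a common odds ratio (OR) of 2 at every cut-point.

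Example with 70/20/10:

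- Any event: odds 0.30/0.70 = 0.429, doubled to 0.857, probability 0.857/1.857 = 0.462.
- Top level: odds 0.10/0.90 = 0.111, doubled to 0.222, probability 0.222/1.222 = 0.182.
- Shifted arm: 53.8/28.0/18.2.

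**Simulated power, 75 per arm, two-sided 0.05, OR 2.**

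| Levels | Reference arm, % | Chi-square | Rank-sum | Gap, points |
|---|---|---|---|---|
| 3 | 70/20/10 | 45% | 55% | 10 |
| 3 | 80/15/5 | 36% | 46% | 10 |
| 3 | 90/8/2 | 22% | 30% | 8 |
| 4 | 70/15/10/5 | 39% | 56% | 17 |
| 4 | 90/6/3/1 | 17% | 30% | 13 |
| 5 | 70/15/10/4/1 | 34% | 56% | 22 |
| 5 | 80/10/6/3/1 | 26% | 47% | 21 |
| 5 | 50/25/15/8/2 | 41 to 42% | 64% | about 22 |

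Repeated runs differ by about a point. With no true difference (OR 1), rank-sum rejected in about 5% of trials. Chi-square rejected in about 3 to 4% in the 5-level settings, where sparse cells make it conservative.

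**Analytic check.** A noncentrality that gives 56% power on 1 df gives 46% on 2 df, 40% on 3 df and 36% on 4 df, close to the three rows with 70% in the lowest level. For 80% power the noncentrality needed is 7.85 on 1 df and 11.94 on 4 df; 11.94 / 7.85 = 1.52, or about 52% more patients for the same one-directional effect.

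**Sensitivity.**

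- *Effect size.* Over odds ratios of 1.5 to 3 and the distributions tried, the gap ran from about 4 to 24 points. At OR 3 with 70/20/10 it is only 88% against 93%.
- *Non-monotone difference.* For 70/20/10 against 55/40/5 the ranking reverses: chi-square 70%, rank-sum 32%.

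**The case against.** Four objections have force.

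1. **The size is assumed.** A reader might take a single pair such as 34% and 56% as a property of this trial. The documents do not support that: they give no levels, frequencies or target effect, and with 3 levels the gap at OR 2 is about 10 points or less.
2. **Most of the loss is from degrees of freedom.** In the 70/15/10/4/1 scenario, a plain chi-square of any event against none reaches 55%, against 56% for rank-sum. This stands. It explains the mechanism but does not rescue the stated test, which is applied across all levels. Collapsing to any event would also discard the grading that the endpoint is meant to record.
3. **Chi-square is not always the weaker test.** The non-monotone example shows this. But the safety hypothesis concerns an increase, and a directional comparison fits that better.
4. **The scope is narrow.** A reader might infer that the whole safety comparison is weakened. It is not: bradycardia, hypotension, hypoxemia, airway maneuvers and apnea are essentially yes/no, and ordering costs chi-square nothing there. Nor do the documents clearly bring shock or dose counts under the rule. The plan never classes the number of shocks as categorical. Re-dosing is listed as an outcome without a count, and the number of extra doses appears only on the Randomization Form.

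A reader might also infer that event-free patients are dropped. The plan does not say so; it is silent on how they are coded.

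**Conclusion.** The point holds for World SIVA severity alone. The plan assigns an ordered safety grade to a test that ignores order. For a consistent shift to worse severity, an ordinal test had more power in every scenario tried: roughly 8 to 22 percentage points at 75 per arm and a common odds ratio of 2, depending on the number of levels and their frequencies. Those inputs are assumptions, so the figures should be read as a range.

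This is a modest improvement to a secondary safety analysis. Even at the rank-sum figures of 30% to 64%, a non-significant result would not by itself show that there is no increase in harm. The trade-off is lower sensitivity to non-monotone differences, which the safety hypothesis does not target.

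**What to change.** In the Analytical Plan, take SIVA severity out of the general rule for categorical variables and state that:

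- its levels are defined in advance, under one variable name used throughout;
- every randomised patient receives a grade, with no event as the lowest level;
- arms are compared with the Wilcoxon rank-sum test, which the plan already uses for non-normal continuous data, or with a proportional-odds model;
- the result is reported as a common odds ratio, or the probability of a worse outcome, with a 95% confidence interval;
- counts and percentages remain as description.

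Chi-square can stay for the yes/no endpoints. The cost is a sentence or two of wording and no additional patients. The readable case report forms show no SIVA field, but parts of the Cardioversion Procedure form are missing from the text available, so the trial team should confirm that a grade is captured for every patient.
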